LIVER EVENTS	ALT or AST $> 5 \times \text{ULN}$ AP $> 2 \times \text{ULN}$ (in the absence of known bone pathology) TBL $> 2 \times \text{ULN}$ (in the absence of known Gilbert syndrome) ALT or AST $> 3 \times \text{ULN}$ and INR > 1.5 Potential Hy's Law cases (defined as ALT or AST $> 3 \times \text{ULN}$ and TBL $> 2 \times \text{ULN}$ [mainly conjugated fraction] without notable increase in AP to $> 2 \times \text{ULN}$) Any clinical event of jaundice (or equivalent term) ALT or AST $> 3 \times \text{ULN}$ accompanied by (general) malaise, fatigue, abdominal pain, nausea, or vomiting, or rash with eosinophilia Any adverse event potentially indicative of a liver toxicity*

*These events cover the following: hepatic failure, fibrosis and cirrhosis, and other liver damage-related conditions; the non-infectious hepatitis; the benign, malignant and unspecified liver neoplasms

INR=International normalized ratio

Table 13-2 Follow-Up Requirements for Liver Events and Laboratory Triggers

Criteria	Actions required	Follow-up monitoring
Potential Hy's Law case ^a	Discontinue the study treatment immediately Hospitalize, if clinically appropriate Establish causality Record AE/SAE and any contributing factors (concomitant medications, other co-morbid conditions/procedures) in the appropriate CRFs	ALT, AST, TBL, Alb, PT/INR, AP and GGT until resolution ^c (frequency at Investigator discretion)
ALT or AST $> 8 \times \text{ULN}$	Discontinue the study treatment immediately Hospitalize if clinically appropriate Establish causality Record AE/SAE and any contributing factors (concomitant medications, other co-morbid conditions/procedures) in the appropriate CRFs	ALT, AST, TBL, Alb, PT/INR, AP and GGT until resolution ^c (frequency at Investigator discretion)

Criteria	Actions required	Follow-up monitoring
> 3 × ULN and INR > 1.5	Discontinue the study treatment immediately Hospitalize, if clinically appropriate Establish causality Record AE/SAE and any contributing factors (concomitant medications, other co-morbid conditions/procedures) in the appropriate CRFs.	ALT, AST, TBL, Alb, PT/INR, AP and GGT until resolution ^c (frequency at Investigator discretion)
> 5 to ≤ 8 × ULN	Repeat LFT within 48 hours If elevation persists, continue follow-up monitoring If elevation persists for more than 2 weeks, discontinue the study drug Establish causality Record AE/SAE and any contributing factors (concomitant medications, other co-morbid conditions/procedures) in the appropriate CRFs	ALT, AST, TBL, Alb, PT/INR, AP and GGT until resolution ^c (frequency at Investigator discretion)
> 3 × ULN accompanied by symptoms ^b	Discontinue the study treatment immediately Hospitalize if clinically appropriate Establish causality Record AE/SAE and any contributing factors (concomitant medications, other co-morbid conditions/procedures) in the appropriate CRFs	ALT, AST, TBL, Alb, PT/INR, AP and GGT until resolution ^c (frequency at Investigator discretion)
> 3 to ≤ 5 × ULN (patient is asymptomatic)	Repeat LFT within the next week If elevation is confirmed, initiate close observation of the patient	Investigator discretion Monitor LFT within 1 to 4 weeks
ALP (isolated)		
> 2 × ULN (in the absence of known bone pathology)	Repeat LFT within 48 hours If elevation persists, establish causality Record AE/SAE and any contributing factors (concomitant medications, other co-morbid conditions/procedures) in the appropriate CRFs	Investigator discretion Monitor LFT within 1 to 4 weeks or at next visit
TBL (isolated)		
> 2 × ULN (in the absence of known Gilbert syndrome)	Repeat LFT within 48 hours If elevation persists, discontinue the study drug immediately Hospitalize if clinically appropriate Establish causality Record AE/SAE and any contributing factors (concomitant medications, other co-morbid conditions/procedures) in the appropriate CRFs	ALT, AST, TBL, Alb, PT/INR, AP and GGT until resolution ^c (frequency at Investigator discretion) Test for hemolysis (eg, reticulocytes, haptoglobin, unconjugated [indirect] bilirubin)

Criteria	Actions required	Follow-up monitoring
> 1.5 to $\leq 2 \times$ ULN (patient is asymptomatic)	Repeat LFT within the next week If elevation is confirmed, initiate close observation of the patient	Investigator discretion Monitor LFT within 1 to 4 weeks or at next visit
Jaundice	Discontinue the study treatment immediately Hospitalize the patient Establish causality Record AE/SAE and any contributing factors (concomitant medications, other co-morbid conditions/procedures) in the appropriate CRFs	ALT, AST, TBL, Alb, PT/INR, AP and GGT until resolution ^c (frequency at Investigator discretion)
Any AE potentially indicative of a liver toxicity*	Consider study treatment interruption or discontinuation Hospitalization if clinically appropriate Establish causality Record AE/SAE and any contributing factors (concomitant medications, other co-morbid conditions/procedures) in the appropriate CRFs	Investigator discretion

^aElevated ALT/AST $> 3 \times$ ULN and TBL $> 2 \times$ ULN but without notable increase in AP to $> 2 \times$ ULN

^b(General) malaise, fatigue, abdominal pain, nausea, or vomiting, or rash with eosinophilia

^cResolution is defined as an outcome of one of the following: (1) return to baseline values, (2) stable values at three subsequent monitoring visits at least 2 weeks apart, (3) remain at elevated level after a maximum of 6 months, (4) liver transplantation, and (5) death.

PT=prothrombin time

14 Appendix 2: Specific Renal Alert Criteria and Actions

Table 14-1 Specific Renal Alert Criteria and Actions

Serum Event	
Serum creatinine increase 25-49% compared to baseline	Confirm 25% increase after 24-48 hours Follow-up within 2-5 days
Acute Kidney Injury: Serum creatinine increase ≥ 50% compared to baseline	Follow-up within 24-48h if possible Consider study treatment interruption Consider patient hospitalization/specialized treatment
Urine Event	
New dipstick proteinuria ≥ 1+ Albumin- or Protein-creatinine ratio increase ≥ 2-fold Albumin-creatinine ratio (ACR) ≥ 30 mg/g or ≥ 3 mg/mmol Protein-creatinine ratio (PCR) ≥ 150 mg/g or > 15 mg/mmol	Confirm value after 24-48 hours Perform urine microscopy Consider study treatment interruption/or discontinuation
New dipstick glycosuria ≥ 1+ not due to diabetes	Blood glucose (fasting) Perform serum creatinine, ACR
New dipstick hematuria ≥ 1+ not due to trauma or menstruation	Urine sediment microscopy Perform serum creatinine, ACR
For all renal events:	
Record AE/SAE and any contributing factors (concomitant medications, other co-morbid conditions/procedures) in the appropriate CRFs.	
Monitor patient regularly (frequency at Investigator's discretion) until either: Event resolution: sCR within 10% of baseline or protein-creatinine ratio within 50% of baseline, or Event stabilization: sCR level with ±10% variability over last 6 months or protein-creatinine ratio stabilization at a new level with ±50% variability over last 6 months.	

15 Appendix 3: Safety monitoring Guidance

15.1 Guidance on monitoring of patients with symptoms of neurological deterioration suggestive of PML

Should a patient develop any unexpected neurological or psychiatric symptom/signs in the opinion of Investigator (eg cognitive deficit, behavioral changes, cortical visual disturbances or any other neurological cortical symptoms/signs any symptom/sign suggestive of an increase of intracranial pressure) or accelerated neurological deterioration, the Investigator should schedule a complete physical and neurological examination and an MRI as soon as possible before beginning any steroid treatment. Conventional MRI as defined in the protocol as well as additional scanning such as Fluid-Attenuated Inversion Recovery (FLAIR) and Diffusion-weighted imaging (DWI) sequences are recommended to aid in differential diagnosis. The MRI must be evaluated by the local radiologist/neurologist. The Investigator will contact the Medical Advisor at Novartis to discuss findings and diagnostic possibilities as soon as possible. A copy of the unplanned MRI should be sent to the MRI Evaluation Center designated by the Sponsor as soon as possible. AE/SAEs need to be filed as appropriate.

If the MRI shows new MS lesions consistent with a [REDACTED]

[REDACTED]. In case of new findings in the MRI images in comparison with the previous available MRI which are not compatible with MS lesions, the study drug will be discontinued and other diagnostic evaluations need to be performed at the discretion of the Investigator. If new lesions are detected on the MRI which may be infectious in origin it is recommended to collect a cerebrospinal fluid sample if indicated. Analysis of the Cerebrospinal fluid (CSF) sample including cellular, biochemical, PCR, and microbiological analysis (eg herpes virus, JC virus) to confirm/exclude an infection should be performed. In the event of suspected CNS infection (PML), a CSF aliquot should be sent to a central laboratory (designated by the Sponsor) for confirmatory testing.

Only after the evaluations have excluded diagnoses other than MS and after discussion with the Medical Advisor at Novartis, the study drug may be restarted.

15.2 Guidance on monitoring of patients with infections

All infections that develop during the study will be reported as AEs on the appropriate CRF capturing AEs. Treatment and additional evaluations will be performed at discretion of the Investigator.

The Investigator should remind the patient of the risk of infections and instruct them to promptly report any symptoms of infections to the Investigator. The patients must also be reminded to always carry their Patient Information Card (with site contact information and which identifies them as participants in a clinical study with investigational and control agents with potential immunosuppressive effects) and to show this to any local healthcare provider they may consult and ask that the Investigator be contacted.

In the case of suspected or confirmed serious (CTCAE, Grade 3-4) or atypical infection, study drug interruption should be considered. The Investigator should inform the Sponsor Medical Advisor of any such cases.

[REDACTED]

When evaluating a patient with a suspected infection, the most sensitive tests available should be used (ie that directly detect the pathogen, as with PCR).

The Investigator should consider early treatment with specific antimicrobial therapy on the basis of clinical diagnosis or suspicion thereof in consultation with infectious disease experts, as appropriate. The Investigator should inform the Sponsor Medical Advisor of any such cases.

Investigators should consider the added immunosuppressive effects of corticosteroid therapy for treatment of MS attack/relapse and increase vigilance regarding infections during such therapy and in the weeks following administration.

In oncology patients treated with ofatumumab, cases of fatal HBV reactivation and fatal infection due to hepatitis B in patients who have not been previously infected have occurred (refer to local ARZERRA® prescribing information). This study excludes the patients who are at potential risk of HBV reactivation (See [Section 4.2](#) Exclusion criterion 11). In patients with suspicion of HBV infection during the study, laboratory testing for HBV should be done. For patients who show new evidence of HBV infection [HBs antigen positive (regardless of antibody status) or HBs antigen negative but HBc IgM/IgG antibody positive], the Investigator is advised to consult with physicians with expertise in managing hepatitis B regarding monitoring and consideration for HBV antiviral therapy.

Patients with new active HBV infection should immediately discontinue study drug and institute appropriate treatment and follow-up.

15.3 Guidance on immunization

The safety of and ability to generate a primary or anamnestic response to immunization with live, live-attenuated or inactivated vaccines during ofatumumab treatment has not been investigated. The response to vaccination could be impaired due to B-cells depletion.

It is recommended that the Investigator review the patient's immunization history as part of the initial Screening procedure for a patient being considered for treatment with ofatumumab. Vaccination of the patient, in compliance with local area vaccination guidelines for the patient population being treated, is recommended prior to administration of ofatumumab. In particular, prior to administration of ofatumumab, hepatitis B vaccination, in patients with risk factors for hepatitis B infection or in areas with a high prevalence of hepatitis B, as per local area treatment guidelines should be considered.

Administration of live or live-attenuated vaccines must be avoided during and after treatment with ofatumumab and until B-cell counts are normalized.

15.4 Guidance on monitoring of patients with low immunoglobulin levels

After baseline, the immunoglobulin levels (IgM and IgG) will be measured at Week 4 and EOS by the central laboratory. They will only be communicated to the site after baseline in case of notably low levels. A notably low IgG level is defined as a level that is 20% below the LLN and a notably low IgM level is defined as a level 10% below the LLN. Following notification, the immunoglobulin level should be repeated within 2 weeks by the central lab to confirm the reading. If the repeated test confirms the immunoglobulin level to be below the threshold, the

study drug must be discontinued and the immunoglobulin levels needs to be monitored at the Investigator's discretion until levels return back to normal limits. The patient should be evaluated and monitored for infections on a regular basis. Immunoglobulin substitution therapy as pert local medical practice is allowed. Re-initiation of the study drug can only be considered once the immunoglobulin levels are back within normal limits.

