5.5.8 Prohibited medication

Use of the treatments displayed in [Table 5-1](#) is NOT allowed in combination with study treatment, due to increased risk of immunosuppression and confounding of efficacy evaluations.

Exclusionary medications and washout periods for study eligibility are listed in the exclusion criteria ([Section 4.2](#)). Use of excluded medications is not allowed after randomization while the patient is on study medication.

Table 5-1 Prohibited medication

Medication	Action taken
Immunosuppressive/chemotherapeutic medications (including herbal) or procedures, including but not limited to cyclosporine, azathioprine, methotrexate, cyclophosphamide, mitoxantrone, cladribine, lymphoid irradiation and hematopoietic/other stem cell transplantation	Discontinue study treatment, increase vigilance regarding infections. NOTE: Restarting study treatment in patients exposed to these medications is not permitted.
Monoclonal antibodies targeting the immune system, including but not limited to natalizumab, alemtuzumab, daclizumab and B-cell depleting agents such as but not limited to rituximab, ocrelizumab, ublituximab and obinutuzumab	Discontinue study treatment, increase vigilance regarding infections. NOTE: Restarting study treatment after exposure to B-cell depleting agents is not permitted. For others only after consultation with the Sponsor.
Any other immunomodulatory or disease-modifying MS treatment, including but not limited to fingolimod, siponimod, ozanimod, laquinimod, interferon beta, glatiramer acetate, dimethyl fumarate, teriflunomide, leflunomide, intravenous immunoglobulin, plasmapheresis or systemic corticosteroids (except for when given for MS relapse treatment as defined in Section 5.5.6).	Interrupt or discontinue study treatment, increase vigilance regarding infections.
Administration of any live or live-attenuated vaccine (including for measles) is prohibited while patients are exposed to study drug (long-lasting effects of the study drugs should be taken into consideration)	They may be administered when patients are no longer exposed to study drug. Consider risk/benefit and follow local labels

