5.6.2 Discontinuation of study treatment

Discontinuation of study treatment for a patient occurs when study drug is stopped earlier than the protocol planned duration, and can be initiated by either the patient or the Investigator.

The Investigator must discontinue study treatment for a given patient if, on balance, he/she believes that continuation would negatively impact the risk/benefit of trial participation.

Discontinuation of study treatment does not mean discontinuation from study. The patient should return to the site as soon as possible, after discontinuation of study drug, for EOS visit. EOS visit assessments ([Table 6-1](#)) should be completed and results recorded in the CRF. The Investigator must determine the primary reason for the patient's premature discontinuation of study treatment and record this information on the appropriate CRF.

Study treatment must be permanently discontinued under the following circumstances:

- Patient wish (withdrawal of consent [Section 5.6.3](#))
- Pregnancy (see [Section 6.6.6](#) and [Section 7.6](#))
- Use of prohibited treatment ([Table 5-1](#))
- Diagnosis of PML
- Patient with active serious infections or reactivation (eg tuberculosis, hepatitis B or C)
- Skin and/or mucosal reactions which raise the suspicion of severe generalized major skin reactions (Stevens-Johnson syndrome, or toxic epidermal necrolysis-Lyell's syndrome)
- Hypersensitivity to the study medication
- Any situation in which study participation might result in a safety risk to the patient
- Protocol violation that results in a significant risk to the patient's safety
- Emergence of certain adverse events, such as malignancy (except successfully treated basal cell carcinoma, *in situ* squamous cell carcinoma and *in situ* carcinoma of cervix of uterus), liver failure or, serious chronic infection (such as HIV)

- Laboratory abnormalities (eg liver function tests (LFT)) and abnormal test procedure as defined in [Appendix 1](#)
- Severe hypoproteinemia
- Interstitial lung disease or new onset or worsening of pulmonary symptoms, such as persistent cough and dyspnea, with or without associated fever, suspicious of interstitial lung disease
- Non-compliance with study treatment

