2.8.3.2 Other special lab results

Other non-routine laboratory data include pregnancy test results, CD19+ B-cell counts (refer to as B-cell counts), total IgG, total IgM, [REDACTED]

The B-cell counts, total IgG, and total IgM, will be summarized using descriptive statistics by treatment group and visit-window.

[REDACTED]

[REDACTED]

Number and percentage of patients meeting the notable low level criteria in IgG or IgM at least once will be provided by treatment group. A notably low IgG level is defined as a level that is 20% below the LLN (i.e. equal to or less than 80% of the LLN) and a notably low IgM level is defined as a level 10% below the LLN (i.e. equal to or less than 90% of the LLN).

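### The protocol's rules conflict on whether study drug may be restarted after a low-immunoglobulin stop treated with immunoglobulin substitution, and do not say how a substituted level counts towards restart

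*Protocol*

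**What the plan says.** Protocol section 15.4 schedules IgG and IgM after baseline at Week 4 and EOS, with a central-laboratory repeat within 2 weeks when a level is notably low. If the repeat confirms it, "study drug must be discontinued and the immunoglobulin levels needs to be monitored at the Investigator's discretion until levels return back to normal limits". The section continues: "Immunoglobulin substitution therapy as pert local medical practice is allowed. Re-initiation of the study drug can only be considered once the immunoglobulin levels" are in the normal range again. It states no route, product or timing for substitution, and no condition that the level be measured off substitution.

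Three other places in the protocol bear on the same patient:

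- **Glossary.** Study drug discontinuation is the point at which the subject stops the drug permanently.
- **Section 5.5.8 and Table 5-1.** One row of prohibited medication includes "teriflunomide, leflunomide, intravenous immunoglobulin, plasmapheresis or systemic corticosteroids". The action for that row is to interrupt or discontinue study treatment. The surrounding text limits the ban to use in combination with study treatment, while the patient is on study medication.
- **Section 5.6.2.** "Study treatment must be permanently discontinued under the following circumstances"; the list that follows includes use of a Table 5-1 treatment. A patient who discontinues has a prompt EOS visit and then enters Safety FU.

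In the SAP, section 2.8.3.2 states: "The B-cell counts, total IgG, and total IgM, will be summarized using descriptive statistics by treatment group and visit-window". It also counts patients who meet the notably-low criterion on any occasion. No visible text deals with values taken under substitution.

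**The concern.** A patient with a confirmed low level who receives intravenous immunoglobulin falls under several rules with different outcomes. Section 15.4 leaves restart open. Table 5-1 is compatible with an interruption. Section 5.6.2, read literally, closes restart if the infusion counts as use of a prohibited treatment. The glossary closes it for any discontinuation. Section 15.4 also ties restart to a serum level immediately after allowing a therapy that supplies immunoglobulin, so the treatment itself can bring about the condition.

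What is at stake is a patient-level safety decision that sites could make differently. A smaller matter is that a level raised by substitution could enter the by-window IgG and IgM summaries as an ordinary value.

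**Working it through.** The documents give no figure to reproduce. The check sets the rules side by side and then applies the SAP's windowing rules to example patients.

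**Restart rules**

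1. Is substitution during the stop prohibited? No. Table 5-1 bars use together with study treatment, and section 15.4 places substitution after the drug is stopped.
2. May the drug be restarted afterwards? Section 15.4: it can be considered. Table 5-1: interruption is possible, and this row has no bar on restarting, although the two rows above it restrict restart. Section 5.6.2: no, if the infusion is use of a Table 5-1 treatment. Glossary: no, because discontinuation is permanent.
3. Is there a visit path for restart? Section 5.6.2 moves the patient to EOS and Safety FU; no path back to treatment is described.
4. May substitution continue after restart? Section 15.4 is silent. If it were intravenous, the Table 5-1 ban would apply again.
5. Does a substituted level satisfy the restart condition? As worded, yes, because no qualifier excludes it.

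**SAP summaries**

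Inputs: Table 2-4 windows (Week 4 = days 1-56, target 28; Week 12 = days 57-111, target 84); the value closest to target is chosen (section 2.1.2.2); the safety cut-off is 100 days after the last dose. In cases A to C the low result and the last dose are on day 28, so the cut-off is day 28 + 100 = 128. The latest repeat is day 28 + 14 = 42, ignoring laboratory turnaround, which is not stated. Other days are assumptions.

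- **A.** Stopped, EOS day 43, no extra test. Week 4 uses day 28. The first follow-up visit is about day 43 + 84 = 127, outside both windows. There is no Week 12 value.
- **B.** As A, with a discretionary test under substitution on day 70. Day 70 becomes the Week 12 value, but it falls after EOS. SAP section 2.1 and Table 2-1 end the Week 12 CSR safety tables at Week 12 or EOS, and section 2.8.6.1 confines post-discontinuation data to listings. Only the Final CSR could show it.
- **C.** Restarted by day 56 with EOS on day 84. Week 12 uses day 84, possibly a substituted value, and this would reach the Week 12 CSR.
- **D.** First low result on day 84, repeat day 98. Week 12 keeps day 84, before substitution.
- **Early repeat.** With a repeat on day 30 or 35 and EOS the next day, a first follow-up visit at the early edge of its window (84 - 14 = 70 days after EOS) falls on day 31 + 70 = 101 or 36 + 70 = 106. Both lie in the Week 12 window, but again only for the Final CSR.

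Case C arises only if the site follows section 15.4 and does not send the patient to EOS on stopping. The protocol conflict therefore decides whether a substituted value can reach the Week 12 CSR tables.

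**Size, by assumption**

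The shift in an arm mean from one patient is rise / n. For a move from 0.80 to 1.00 x LLN: 0.20/13 = 0.015 x LLN in a thigh arm and 0.20/62 = 0.003 x LLN in an abdomen arm. For an assumed rise of 3 to 6 g/L, which has no source in the documents: 3/13 = 0.23 to 6/13 = 0.46 g/L, and 3/62 = 0.05 to 6/62 = 0.10 g/L. These use the randomised arm sizes.

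**The case against.** The strongest reply is that little can go wrong. Normal levels are a necessary condition for considering restart, not a trigger, and section 5.5.5 leaves restart after an interruption to case-by-case judgement. How to read a level under substitution is a clinical matter. Patients with IgG or IgM below LLN are excluded at entry and planned treatment lasts 12 weeks, so few should meet the stop rule. All of this stands, and it limits the size of the problem. It does not remove the disagreement over whether restart is possible at all.

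A reader might infer that substitution itself breaches Table 5-1. The scope of the ban does not support that, because section 15.4 allows substitution only after the drug is stopped.

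A reader might also infer that the SAP shows the most affected patients as recovered and biases the immunoglobulin readout towards no effect. The documents do not support this either. No visible table defines recovery, and a later value cannot undo the count of patients ever notably low. A low Week 4 value stays in its own window, and values after a stop and early EOS are kept out of the Week 12 CSR tables. Nor do the documents show that substitution raises IgM, so the point is stronger for IgG.

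Finally, SAP section 2.8.3.2 and the title of Table 2-6 are partly redacted, so a rule for such values may already exist. This reservation stands.

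**Conclusion.** The protocol contradicts itself on restart. Section 15.4 leaves re-initiation open after a stop that the glossary calls permanent and that section 5.6.2 routes to EOS and Safety FU. Table 5-1 and section 5.6.2 also disagree on the consequence of intravenous immunoglobulin: interruption is possible under one, and permanent discontinuation is required under the other. As worded, a substituted level can meet the restart condition. The conflict concerns restart and any continuing substitution, not substitution during the stop.

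The statistical consequence is minor. By-window levels and changes from baseline can take a substituted value only in some timings: restart before Week 12, or values reported in the Final CSR. The number of patients is not given and is probably small, and the mean shifts above rest on assumed rises. The notably-low count is unaffected. The bioequivalence analysis uses AUCtau and Cmax, so its test, sample size and error rate do not change.

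**What to change.** **Protocol.** Reconcile section 15.4, Table 5-1, section 5.6.2 and the glossary on whether study drug may be restarted after immunoglobulin substitution. Section 15.4 should also state how a level measured under substitution is to be read. The clinical rule is for the sponsor; the need here is that all four places say the same thing.

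**SAP section 2.8.3.2 (minor).** Unless the redacted text already covers it, flag IgG and IgM values taken on or after the start of substitution, using the concomitant-medication CRF. Give the by-window summaries with and without them, and report the number of patients substituted. Exclusion alone would not be enough, because it would remove the patients with the deepest fall from the later window.

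**Cost.** One protocol clarification, one or two SAP sentences, and one flag derived from data already collected. No new assessments and no change to the primary analysis.
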